13.6.1.4. Secondary endpoints

Secondary endpoints will be compared by treatment group and will not be adjusted for multiplicity. Analysis methods for these endpoints will be described in the SAP. These analyses will be performed using observed data in the FAS. The secondary endpoints include change from baseline to Week 4 for 17-OHP and changes from baseline to Week 24 in:

- Blood pressure
- Glucose tolerance (subjects without diabetes mellitus)
- Waist circumference
- Menstrual regularity (women not using hormonal or IUD contraception only)
- TART size and characteristics (men only)

An additional secondary endpoint is the percent change from Month 12 in glucocorticoid daily dose (in hydrocortisone equivalents adjusted for BSA [mg/m²/day]) at Month 18, while Month 18 androstenedione is adequately controlled at \leq 120% of baseline or \leq ULN for age and sex. This additional secondary endpoint will be compared by treatment group randomly assigned at Month 12 and will not be adjusted for multiplicity. Analysis methods for this endpoint will be described in the SAP. This analysis will be performed using observed data and restricted to subjects with a glucocorticoid daily dose (in hydrocortisone equivalents adjusted for BSA [mg/m²/day]) $>$ 14 mg/m²/day at Month 12 in the RAS.

13.6.2. Safety Analyses

Safety data from the double-blind, placebo-controlled period through Week 24, the open-label period through Month 12, the double-blind, active-controlled period through Month 18 for those subjects who were re-randomized, and the open-label extension treatment period from Month 18 onwards will be analyzed separately. The subject incidence of treatment-emergent adverse events will be tabulated by randomized treatment group assignment at baseline or at Month 12, as appropriate, for adverse events, serious adverse events, fatal adverse events, and adverse events leading to discontinuation of study drug. Descriptive statistics by randomized treatment group assignment at baseline or at Month 12, as appropriate, will be generated for additional safety data, including selected laboratory analytes, vital signs, ECG parameters, C-SSRS, and BPRS. The safety analyses described above will also be generated for safety data collected during the open-label extension period by crinecerfont dose level and all subjects combined.

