Starting at Month 18, all subjects who are continuing in the OLE will initially receive open-label crinecterfont 100 mg bid. If the subject has inadequate disease control despite receiving glucocorticoid treatment at their target dose (in the opinion of the investigator), the crinecterfont dose may be increased to 100 mg qAM and 200 mg qPM (including at Month 18, after laboratory results are available). If the increased dose of 100 mg qAM and 200 mg qPM is not

well tolerated, the dose may be reduced back to 100 mg bid. After the Month 24 visit, an alternative dosing regimen of once daily 200 mg qPM can be considered per the investigator ([Appendix C](#)). Crinecerfont doses should generally only be adjusted at or shortly after study visits (after laboratory results are available).

In the setting of inadequate disease control, if the glucocorticoid dose is at or above the target, an increase in the glucocorticoid dose should generally be considered only after the crinecerfont dose has been maximized for the subject. Changes to the glucocorticoid and crinecerfont doses should generally be separated by at least 1 month in order to assess the effect of each change.

Study visits during the OLE will occur every 3 months until Month 24, and every 6 months thereafter, with the option of having the Month 21 visit at home.

At the Month 24 visit, and every 12 months thereafter, subjects will have blood sample collection before and approximately 2 hours after dosing of morning glucocorticoid and study drug at the study site. Subjects should be fasting from the night before (subjects should be encouraged to drink water to avoid any hypovolemic status). A glucose tolerance test will also be performed at Month 24 and every 12 months thereafter (with study drug taken with the glucose load rather than a meal).

Subjects will remain in the OLE until crinecerfont becomes commercially available, the Sponsor elects to discontinue development of crinecerfont for CAH, the Sponsor elects to discontinue the study, or the subject meets one of the study withdrawal criteria.

Follow-Up Period

A final posttreatment visit will be conducted approximately 1 month after subjects' final dose of study drug. This visit is not required if the subject transitions during the OLE to taking commercially-available crinecerfont or to another crinecerfont study.

[figure not shown]
Study Assessments and Study Visit Scheduling

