9.8. Study Duration

The expected duration of study participation for each subject is approximately 20 months, plus a variable amount of time in the OLE (estimated average of approximately 24 months), including 1 month for screening, 6 months of blinded placebo-controlled treatment, 6 months of open-label treatment, 6 months of open-label or blinded active-controlled treatment, a variable amount of time of open-label extension period treatment, and 1 month of follow up.

The end of the study is defined as the date of the last visit shown in the Schedule of Assessments for the last subject in the study globally.

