10. STUDY DRUG

10.1. Crinecerfont

Crinecerfont will be supplied as capsules containing 50 mg of crinecerfont free base for oral administration. Subjects will administer 100 mg bid (200 mg total daily dose). Subjects with glucocorticoid dose $>11 \text{ mg/m}^2/\text{day}$ at Month 12 will be re-randomized to continue crinecerfont at 100 mg bid or adjust their crinecerfont dose to 100 mg qAM and 200 mg qPM.

Starting at Month 18, all subjects who are continuing in the OLE will initially receive open-label crinecerfont 100 mg bid. If the subject has inadequate disease control despite receiving glucocorticoid treatment at their target dose (in the opinion of the investigator), the crinecerfont dose may be increased to 100 mg qAM and 200 mg qPM (including at Month 18, after laboratory results are available). If the increased dose of 100 mg qAM and 200 mg qPM is not well tolerated, the dose may be reduced back to 100 mg bid. After the Month 24 visit, an alternative dosing regimen of once daily 200 mg qPM can be considered per the investigator ([Appendix C](#)). Crinecerfont doses should generally only be adjusted at or shortly after study visits (after laboratory results are available).

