### **11.2.5. Exposure-Adjusted Subject Incidence Rate**

Exposure-adjusted subject incidence rate will be defined as the number of unique subjects experiencing the TEAE one or more times (numerator) divided by the sum of the time at risk for the first TEAE across all subjects (denominator). For subjects experiencing the TEAE, the time at risk (exposure time) is the time from the first dose to the date of the first occurrence of the TEAE. For subjects not experiencing the TEAE, exposure time is the time from the first dose to the last dose + 28 days (or data cutoff). Note that exposure time will vary across subjects for the

same TEAE. The exposure-adjusted subject incidence rate in the crinecerfont and placebo groups will be summarized by descending preferred term in the crinecerfont group.

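### Open-label extension adverse events are planned as subject incidence by crinecerfont dose level, although time on each level differs between subjects; add person-time and an attribution rule

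*Protocol*

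**What the plan says.** Protocol Section 13.6.2 sets the measure: "The subject incidence of treatment-emergent adverse events will be tabulated by randomized treatment group assignment at baseline or at Month 12, as appropriate". It then carries these analyses into the open-label extension (OLE), where they "will also be generated for safety data collected during the open-label extension period by crinecerfont dose level and all subjects combined". It gives no person-time denominator and no rule for which level an event belongs to when a subject has changed dose.

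The levels open as follows.

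- **100 mg bid:** "Starting at Month 18, all subjects who are continuing in the OLE will initially receive open-label crinecerfont 100 mg bid" (Section 10.1).
- **100 mg qAM/200 mg qPM:** allowed for inadequate disease control, from Month 18 once laboratory results are in, with a return to bid if poorly tolerated (Section 10.1).
- **200 mg qPM:** "After the Month 24 visit, an alternative dosing regimen of once daily 200 mg qPM can be considered per the investigator" (Section 7).

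Appendix C allows moves in several directions according to the investigator's view of control, including from 200 mg qPM back to bid or up to 100/200 mg. Section 9.8 estimates an average OLE of about 24 months.

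SAP Section 1 leaves OLE summaries to a separate SAP. SAP Section 11.2.5 already has a person-time measure: "Exposure-adjusted subject incidence rate will be defined as the number of unique subjects experiencing the TEAE one or more times", divided by summed time at risk. It is reported for the crinecerfont and placebo groups.

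**The concern.** A percentage of subjects with an event compares groups fairly only if the groups are followed for similar times. OLE dose level is a time-varying exposure chosen by the investigator. One subject can enter two or three denominators for very different lengths of time. A level on which subjects stay longer collects more first events even if it carries no more risk. Poor tolerability can also shorten time on 100/200 mg, so exposure is not independent of harm.

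The term dose level is itself ambiguous: the synopsis gives 100 mg bid and 200 mg qPM the same total daily dose of 200 mg, so a table by dose level could pool them or separate them.

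At stake is how the long-term harm tables by regimen are read. The OLE is the only source of data on 200 mg qPM. No efficacy conclusion is affected.

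**Working it through.** The documents give no OLE incidence or person-time, so there is no planned figure to reproduce. The check asks what the planned table would show if the regimens did not differ in risk.

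**Inputs from the protocol.** OLE from Month 18 to about Month 42 (24 months on average, Section 9.8); bid and 100/200 mg available from Month 18; 200 mg qPM after Month 24. The maximum windows are therefore 24 months for bid and 42 − 24 = 18 months for qPM.

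**Assumptions.** A constant hazard r, equal on all regimens, at 0.05, 0.3 or 1.0 first events per person-year; a switch to qPM at Month 24 or Month 30; 10% to 75% of subjects switching. None of these is in the documents.

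**Formula.** Crude incidence after t months = 1 − exp(−r × t/12), and the ratio is bid divided by qPM. For r = 0.05: 24 months gives 1 − exp(−0.10) = 9.5%, 18 months gives 1 − exp(−0.075) = 7.2%, and 6 months gives 1 − exp(−0.025) = 2.5%.

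| Months on bid vs qPM | r = 0.05 | r = 0.3 | r = 1.0 |
|---|---|---|---|
| 24 vs 18: bid throughout vs subjects on qPM from Month 24 | 1.32 | 1.25 | 1.11 |
| 6 vs 18: same subjects, all switching at Month 24 | 0.34 | 0.38 | 0.51 |
| 24 vs 12: bid throughout vs subjects on qPM from Month 30 | 1.95 | 1.74 | 1.37 |
| 12 vs 12: same subjects, all switching at Month 30 | 1.00 | 1.00 | 1.00 |

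In the first row the ratio tends to 24/18 = 1.33 as the event becomes rare and cannot exceed it.

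**Mixed population, switch at Month 24, r = 0.05.** If a fraction p switches, bid incidence is (1 − p) × 9.52% + p × 2.47%, against 7.23% on qPM. The ratio is 1.22, 1.07, 0.83 and 0.59 for p = 10%, 25%, 50% and 75%. It crosses 1 at p = (9.52 − 7.23)/(9.52 − 2.47) = 0.32. With fewer than about a third switching, bid looks worse; with more, qPM does. If 20% are also moved to 100/200 mg at Month 21 and 75% switch to qPM, the ratio is 0.36.

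**100/200 mg against bid.** Both can start at Month 18, so their maximum windows are equal and no ratio is built in. Any imbalance comes from when subjects change.

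**With person-time.** The expected number of subjects with an event is proportional to 1 − exp(−rt), and expected time to first event or end of window to [1 − exp(−rt)]/r. Their quotient is r on every regimen, so the expected ratio is 1.00 in all the scenarios above.

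**Month length.** The protocol counts months as 4 weeks, so 24 months is 24 × 28/365.25 = 1.84 years rather than 2. The time ratios, and hence the 1.33 ceiling, do not change; the effective rates shrink by about 8%.

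**The case against.** The strongest reply is that Section 13 of the protocol is an outline and the OLE analyses belong to a separate SAP that may already contain person-time and an attribution rule. Section 13.6.2 does not exclude exposure adjustment, and SAP 11.2.5 shows that the sponsor already uses the method. This stands as a reason to rate the point low. It does not remove it, because 13.6.2 fixes the measure and the grouping, and 11.2.5 as written counts from first dose to last dose plus 28 days without splitting time at a regimen change.

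Three stronger readings are tempting and are not supported.

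- **A roughly two-fold distortion.** A reader might infer this from 6 months on bid against 18 on qPM. That assumes every subject switches at Month 24, whereas the protocol only lets the investigator consider it.
- **Different windows for all levels by design.** Only 200 mg qPM opens late.
- **Different observation by dose.** A reader might take this from "Study visits during the OLE will occur every 3 months until Month 24, and every 6 months thereafter". The schedule follows study month for everyone, and adverse events are recorded continuously from consent to the final visit (Section 11), so it adds little for adverse events.

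It is also true that 100/200 mg is compared with bid in a randomised, blinded period from Month 12 to Month 18, analysed separately, and that no OLE dose comparison is among the study objectives. Nor does person-time remove selection: subjects on 100/200 mg are there because control was inadequate, and 200 mg qPM is meant for those with adequate control (Section 5.3).

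**Conclusion.** The point holds in a limited form. Equal hazards can give unequal crude incidences by dose level, and the direction is not fixed. Across the 24-month scenarios with r from 0.05 to 1.0 per person-year, the bid/qPM ratio lies between about 0.34 and 1.95. Only the ceiling of 1.33 for the maximum windows follows from the protocol's own timing; everything beyond it rests on assumed switch times and switching fractions. The missing attribution rule and the ambiguity of dose level need no such assumptions. Whether the separate OLE SAP closes the gap cannot be judged from the supplied documents. This is a cheap improvement, not a threat to the trial's conclusions.

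**What to change.** In Protocol 13.6.2 and in the separate OLE SAP:

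1. Attribute each OLE adverse event to the regimen in use at onset.
2. Beside the crude percentages, report exposure-adjusted subject incidence rates with person-years per regimen, adapting SAP 11.2.5 so that time at risk is split at each regimen change.
3. Replace dose level by three named regimens: 100 mg bid, 100 mg qAM/200 mg qPM, and 200 mg qPM.
4. Footnote the tables: regimens are non-randomised and chosen on disease control, which person-time does not correct.

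The cost is a few sentences and minor programming. Person-year rates are less familiar to readers than percentages, which is why the percentages stay alongside. No dosing or visit rule changes.

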13.7. Week 24 Interim Analysis

An unblinded interim analysis on the primary endpoint using the “promising zone” method ([Mehta and Pocock, 2011](#)) will be conducted when approximately the first 83 subjects (approximately 50% of the planned number of enrolled subjects) have had the opportunity to complete the Week 24 assessments. The primary endpoint will be analyzed in a similar fashion at the interim analysis and at the final analysis using an ANCOVA model as described in [Section 13.6.1.2](#). The interim analysis will be conducted by an independent statistical center (ISC) and will be evaluated by the DMC. The DMC will assess futility and consider sample size re-estimation based on the observed treatment effect and the conditional power at the time of the interim analysis. Conditional power is the probability that, conditional on the current value of the test statistic at the interim analysis, the study will achieve statistical significance at the final analysis. The adaptive elements of this interim analysis and the criterion for each DMC recommendation are detailed in an Adaptation Plan. Access to the Adaptation Plan will be limited to the ISC, DMC, and selected Sponsor staff assigned to the crinecerfont program, specifically the biostatisticians, regulatory lead, and program team lead.

Based on the interim analysis results, one of the following recommendations will be made by the DMC:

- Stop the study for futility
- Continue the study to the planned sample size
- Increase the sample size to a maximum of 210 subjects

The DMC will communicate the recommendation, without disclosing the numerical results, to a very limited number of Sponsor personnel or their designees who are not directly involved with the conduct or oversight of the study and will include a biostatistician and a clinician.

13.8. Week 24 Final Analysis

The final unblinded analysis of the double-blind, placebo-controlled period will be conducted once all subjects have completed the Week 24 visit. Data through Week 24, including the primary, key secondary, and secondary endpoints, will be analyzed. Since this analysis includes all data for the primary and key secondary endpoints, there will be no adjustments to the level of significance and the full 0.05 level of significance will be used. Following this analysis, the subject, investigator, all study center personnel, and Sponsor personnel with direct contact with the site will continue to be blinded to the subject’s blinded treatment assignment ([Section 10.7](#)).

13.9. Month 12 and Month 18 Final Analyses

The final analysis of the open-label period will be conducted once all subjects have completed their Month 12 visit. At this time, all data collected from Week 24 up to Month 12 will be analyzed.

The final unblinded analysis of the open-label or double-blind, active-controlled period will be conducted once all subjects have completed the Month 18 visit. Data from Month 12 through Month 18, including the secondary endpoint described in [Section 13.6.1.4](#), will be analyzed. Following this analysis, the subject, investigator, all study center personnel, and Sponsor

personnel with direct contact with the site will continue to be blinded to the subject's blinded treatment assignment.

14. REGULATORY AND ETHICAL ISSUES

14.1. General Legal References

The study will be carried out according to provisions of the US CFR, the US Food and Drug Administration (FDA), the laws and regulations of the country in which the study is conducted, and the ICH Guidelines for GCP. All clinical work conducted under this protocol is subject to GCP regulations. This includes an inspection by the Sponsor or its representative, health authority, or IRB/IEC representatives at any time. The investigator must agree to the inspection of study related records by health authority representatives and/or the Sponsor or its designee.

14.2. Institutional Review Board/Independent Ethics Committee

The final approved protocol and the ICF will be reviewed by the IRB/IEC at the study center. The committee's decision concerning conduct of the study will be sent in writing to the investigator and a copy will be forwarded to the Sponsor. The investigator must agree to make any required progress reports to the IRB/IEC, as well as reports of SAEs, life-threatening problems, or death.

A list of members participating in the IEC/IRB meetings must be provided, including the names, qualifications, and functions of these members. If that is not possible, the attempts made to obtain this information along with an explanation as to why it cannot be obtained or disclosed must be documented in the study documentation.

If a member of the site study personnel was present during an IEC/IRB meeting, it must be clear that this person did not vote.

14.3. Protocol Adherence – Amendments

The protocol must be read thoroughly, and the instructions must be followed exactly. Any changes in the protocol will require a formal amendment. Such amendments will be agreed upon and approved in writing by the investigator and the Sponsor. The IRB/IEC and local health authorities will be notified of all amendments to the protocol in accordance with local regulations.

Modifications made to the protocol or the ICF after receipt of the approval must also be submitted as amendments by the investigator and/or sponsor/CRO to the IEC/IRB and to the national competent (health) authority in accordance with local procedures and regulations.

14.4. Required Documents

The investigator must provide NBI or its designee with the following documents before the enrollment of any subject (originals should be kept by the investigator in the investigator's study regulatory document binder):

- Signed copy of the protocol signature page.
- Investigator's Brochure acknowledgement page.
- Completed and signed statement of investigator qualifications, as applicable.
- Financial disclosure documentation as required.
- Curriculum vitae and current medical license of the investigator and subinvestigators.
- Letter of approval from the IRB/IEC for protocol and consent form.
- Copy of the IRB/IEC approved written ICF to be used.
- Laboratory documents (certifications/accreditations, normal ranges) if not provided by a central laboratory.

14.5. Informed Consent

Prior to any study-related procedures, subjects must provide written informed consent (which may be done remotely, if allowed and remote consenting procedures are in place), as required by the governing IRB/IEC and according to local laws and regulations. Prior to any OLE-related study procedures, subjects will review applicable portions of the informed consent form and confirm whether they will participate in the optional OLE.

Each subject's chart will include the signed ICF for study participation. When the study treatment is completed and the eCRF has been monitored, the ICF will be kept in the investigator's central study file. Regulatory authorities may check the existence of the signed ICF in this central study folder if not having done so during the study.

14.6. Study Monitoring

Throughout the course of the study, the study monitor will make frequent contacts with the investigator. This will include telephone calls and on-site visits. During the on-site visits, the eCRFs will be reviewed for completeness and adherence to the protocol. As part of the data audit, source documents will be made available for review by the study monitor. The study monitor will also perform drug accountability checks and may periodically request review of the investigator study file to ensure completeness of documentation in all respects of clinical study conduct.

Upon completion of the study, the study monitor will arrange for a final review of the study files after which the files should be secured for the appropriate time period. The investigator or appointed delegate will receive the study monitor during these on-site visits, will cooperate in providing the documents for inspection, and will respond to inquiries. In addition, the investigator will permit inspection of the study files by authorized representatives of the regulatory agencies.

